7.8 MANAGEMENT OF CONFOUNDING FACTORS

No confounding factor was identified.

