6.2.1.3 Precautions for use

For external use only and for use on a limited area, due to the presence of Salicylic Acid. For adults only.

- Skin preparation is recommended 15 days before the first peel.
- Must only be used by trained healthcare professionals. Required knowledge of complications associated with the application of medical devices and how to react is necessary.
- Always use protective gloves during the procedure and clean the glass cup carefully between each peel session. Cotton buds should be disposed of after each use.
- Do not use alcohol or acetone-based cleanser.
- Avoid the lip area and nasolabial folds. Do not swallow.
- Avoid eyes and mucous membranes: in the event of accidental contact, rinse thoroughly with water, and use a saline solution.
- Avoid sun exposure and use sun protection (K Ceutic or Sun Ceutic 50+) for 4 weeks after the treatment and in-between treatments.
- Keep out of the reach of children.
- In case of alteration in the product's appearance, do not use the medical device.
- Protocol variations should be based on assessment of patient skin type, treatment tolerance and desired results.
- Do not apply on a large area or other areas of the body to avoid a high absorption of Salicylic Acid.
- Never hold the medical device above the patient to avoid accidental spillage.
- If an allergic reaction is considered likely, apply the product to a 1 cm² sized area behind the ear, following the exact same protocol. If no unusual reaction is observed within 72 hours, the facial peel can go ahead.

The practitioners are asked to refer to the last version available of IFU/IB.

6.2.2 List of other medical device or medication to be used during the clinical investigation

No other medical device or medication is planned to be used according to the CIP. However the associated cosmetic products are to be used during the investigation.

Accompanying products are commercially available products developed by DERMOSCIENCES LTD. They are used to prepare and protect the skin during the peeling procedures and to maintain the effect of the peeling.

Foamer 15 (15 % glycolic acid foamer):

- Use as a pre-peel: Cleanse the face with 4 squeezes spread over the whole face, rinse thoroughly after 2 minutes or as soon as the first tingling appears and dry.
- Use at home: Apply a small amount of foam to the clean and dry face.

Massage and rinse with water after two minutes or as soon as you start to feel tingling.

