- Precautions: You may feel a tingling sensation. If discomfort occurs, reduce the frequency of use.
- Do not apply to irritated or damaged skin, or to the eyes and mucous membranes.

Avoid exposure to the sun.

Hyal Ceutic (Intense moisturizing cream):

- Use: Apply when skin needs moisturising, all over the face during the day as required.
- Precautions for use: Avoid contact with eyes and mucous membranes. In case of contact, rinse with plenty of water. Do not apply to open wounds.

Sun Ceutic teintée (SPF 50+ product, slightly tinted):

- Use: Every morning, apply evenly to the face, neck and décolleté 10 minutes before sun exposure. Reapply frequently.
- Precautions for use: Do not apply to irritated or damaged skin, or to the eyes and mucous membranes. In case of contact, rinse with plenty of water. Avoid prolonged exposure to the sun, even with the cream.

DUAL+ (Night cream):

- Use: Apply in the evening to the full face focusing especially on the areas of concern. Increase frequency progressively, up to 2 times per day.

PRECAUTIONS You may experience a tingling sensation, redness and slight desquamation. In case of discomfort, reduce the frequency of use.

DERMOSCIENCES FRANCE	Medical Device CIP # 22E2387	Final version 1.0 Date: 16.08.2022	Confidential Page 26/49
-------------------------	---------------------------------	---------------------------------------	----------------------------

Do not apply to irritated or broken skin. Do not combine this product with other retinol-based products. Avoid direct contact with eyes and mucous membranes.

During use, avoid exposure to sunlight without high SPF protection.

Not recommended for sensitive and/or very dry skin.

NB: All these cosmetic products are in the market

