6.4.1.2 Study schedule

Visit 1: D0

- Subjects will come to the investigational site with their completed diary.
- Information of the subjects on study aims and schedule.
- Signature of consent form in two copies by the subject and the investigator in charge of the screening visit.
- Medical examination for verification of subject's health state, collection of previous medical history, previous and actual treatments.
- A urinary pregnancy test will be performed for women with childbearing potential.
- Checking of inclusion and exclusion criteria.
- Distribution to the subjects of accompany treatment with the instructions of use.
- Colorface standardized photos will be taken by the Technician.
- Acne lesions will be counted by the Investigator.
- Distribution of the ID card and diary so they can note the adverse events and concomitant treatments / acts.

Visit 2, 3 and 4: D15, D36 and D57

- Subjects will come to the investigational site with their completed diary.
- Checking of exclusion criteria.
- Colorface standardized photos will be taken by the Technician.
- Acne lesions will be counted by the Investigator.
- Peeling act will be performed by the Investigator.
- Record of AE and concomitant treatments.

Visit 5: D78

- Subjects will come to the investigational site with their completed diary.
- Checking of exclusion criteria.
- Colorface standardized photos will be taken by the Technician.
- Acne lesions will be counted by the Investigator.
- Subjective questionnaire.
- Scoring of Patient global assessment.
- Score of Investigator global assessment.
- Record of AE and concomitant treatments.

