6.4.4 Description of activities performed by sponsor representatives

The sponsor has delegated the following activities to the CRO (Eurofins Dermascan Pharmascan):

- Overall management of the study: document writing, coordination and training of staff participants, study realization and inclusions status follow-up.
- Submission of the study files to the Ethics Committee (EC) and Competent Authority (CA).
- Management of investigators contracts and fees payment.
- Data management
- Statistical analysis and clinical investigation report writing.

6.4.5 Any known or foreseeable factors that may compromise the outcome of the clinical investigation or the interpretation of results and the methods for addressing these factors

None.

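### Sections 7.8 and 6.4.5 declare no confounder although section 6.2.2 requires active home products alongside the peels, so a fall in lesions cannot be credited to the peel alone

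*Combined protocol and SAP*

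**What the plan says.** Section 7.8, on confounding, reads in full: "No confounding factor was identified". Section 6.4.5 asks for known or foreseeable "factors that may compromise the outcome of the clinical investigation or the interpretation of results" and answers that there are none.

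Section 6.2.2 says of the sponsor's accompanying products: "However the associated cosmetic products are to be used during the investigation". It gives their purpose: "They are used to prepare and protect the skin during the peeling procedures and to maintain the effect of the peeling". Four are listed: Foamer 15 (15% glycolic acid, used before the peel and at home), a moisturiser, a tinted sunscreen, and the night cream DUAL+. For DUAL+ the instruction is "Increase frequency progressively, up to 2 times per day", with a reduction in case of discomfort. Its precautions warn against combining it with other retinol products. Foamer 15 also carries a reduce-for-discomfort line, but no home frequency is given.

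On recording, the Visit 1 schedule in 6.4.1.2 lists "Distribution of the ID card and diary so they can note the adverse events and concomitant treatments / acts". The flow-chart hands out the cosmetics and a daily log in one row at D0, collects the log at V2 to V5, and marks adherence control at all five visits. Under 10.1, subjects are questioned at each visit about topical, systemic or other products.

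The study is open, single-centre and unrandomised, with within-subject comparison (6.1.1, 6.3.6). The hypothesis in 5.4 is that Crystal Peel is effective in mild acne.

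**The concern.** With no control arm, anything that changes over the same weeks as the peels is a rival explanation for a fall in lesions. Here the plan itself supplies such a rival, at a dose that can vary over time and between subjects. It also says that the products help to maintain the peel's effect, which concedes that they bear on the outcome. Elsewhere it treats outside products as a threat: inclusion criterion 8 bars non-study facial products, and exclusion criterion 8 bars treatments that may interfere with the results.

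If 7.8 and 6.4.5 stand, the report can state that nothing competes with the peel as an explanation and conclude for the peel alone. The data would support a conclusion only about the peel used together with the products.

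**Working it through.** **1. The statements side by side.**

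| Topic | Where | Content |
|---|---|---|
| Confounders | 7.8 | none identified |
| Factors affecting interpretation | 6.4.5 | none |
| Required co-treatment | 6.2.2 | four home products, including a glycolic acid foamer and DUAL+ |
| Variable frequency | 6.2.2 | DUAL+ rises, or falls for discomfort; foamer falls for discomfort |
| Control group | 6.1.1, 6.3.6 | none |
| Hypothesis | 5.4 | credits Crystal Peel |
| Analysis or report of product use | section 7 | none |

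The first two rows cannot both be kept with the third to fifth.

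**2. Exposure over time.** Products are handed out at D0. At D15 the schedule lists lesion counting before the first peel.

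- D0 to D15: 15 days, 15/78 = 19% of follow-up, products without peel.
- D15 to D78: 78 − 15 = 63 days, 63/78 = 81%, peels together with products if their use continues.

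The planned contrast is change from the first measurement (7.2.2), which is D0, so every later contrast includes the products-only period. Taking D15 as reference would remove that period but not the overlap in the following 63 days.

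**3. What is recorded.** The stated diary content is adverse events and concomitant treatments or acts. The fields of the daily log and the scope of adherence control are not described. The questioning in 10.1 has no stated frequency or amount item.

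**4. Illustration of size (assumed inputs).** The plan has no effect size, SD or power (7.4), so there is no figure of its own to reproduce. Document inputs: n = 30 evaluable, two-sided α = 0.05. Assumed: a mean count of 30 at D15; products alone lower it by 5%, 10% or 20% from D15 to D78; SD of change 8 to 12; no peel effect.

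- Falls: 30 × 0.05 = 1.5; 30 × 0.10 = 3; 30 × 0.20 = 6 lesions.
- One-sample t test on the change: noncentrality = (fall/SD) × √30, 29 degrees of freedom, critical value 2.045.

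| Fall | SD 12: noncentrality, P(significant) | SD 10 | SD 8 |
|---|---|---|---|
| 1.5 | 0.685, 10% | 0.822, 12% | 1.027, 17% |
| 3 | 1.369, 26% | 1.643, 36% | 2.054, 51% |
| 6 | 2.739, 75% | 3.286, 89% | 4.108, 98% |

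The nominal figure is 5%. The D15 to D78 test is not one that the plan contains; it is used only to isolate the weeks in which peels and products overlap.

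**The case against.** The strongest reply is that product use may well be recorded. The log is issued with the cosmetics and collected at four visits. Subjects never handle the device (10.1), so the home products are an obvious thing for adherence control to cover. Section 6.3.13 ties full compensation to the return of products and log. The flow-chart calls the products associated treatment, and 6.2.3.1 asks for dose and dates of any concomitant treatment. This stands. A reader might infer that the diary omits product use and that change after D15 can never be checked against it. The documents do not show that; they show only that the log's content is undefined and that no report is planned.

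A reader might also infer that all the home products are used at a rising frequency up to D78. Rising frequency is stated for DUAL+ only, with no timetable, and it could be complete before D15. Use to D78 is an inference from the instruction to use the products during the study and from their maintenance purpose. No stop date is given, and the extracted flow-chart row for associated treatment has a single mark, at V2, which may be an extraction fault.

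The illustration is fairly criticised too. Its inputs are assumed, and perfect logging would leave every probability unchanged, because the cause is the missing control. It therefore supports the narrower conclusion, not the logging.

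None of this removes the contradiction between 7.8 and 6.4.5 on one side and 6.2.2 on the other.

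**Conclusion.** The point holds in this form: two statements in the plan are contradicted by its own list of required co-treatments, and the design cannot attribute a fall in lesions to the peel apart from those products. The conclusion rests on the text and the absence of a control, not on any assumed figure.

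How much of an observed fall the products might explain cannot be derived from the documents. The range of 10% to 98% mainly reflects the chosen effect sizes and SDs and should be cited only as an illustration. On recording, the supportable finding is that frequency of home-product use is not specified as an item to be collected or reported. Better records would describe exposure; they would not separate the two effects.

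**What to change.** - Replace the statements in 7.8 and 6.4.5 with one that names the accompanying products as co-interventions whose effect cannot be separated from the peel's in this design.
- Word the efficacy conclusion as *Crystal Peel used with the accompanying products*.
- Add a daily tick per product to the existing log, before enrolment begins, since daily use cannot be reliably reconstructed later.
- Report use descriptively for D0–15, D15–36, D36–57 and D57–78, stating that this describes exposure and does not separate peel from product effects.

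A table of lesion change by pattern of DUAL+ use should not be added. It would split about 30 subjects on a post-baseline variable that can itself reflect reactions to the peel, since use is cut for discomfort and section 4.2 expects redness, burning and desquamation after treatment. Section 7.10 also plans no subgroup analysis.

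The cost is a small block in the diary, one descriptive table and a slightly narrower claim, with no added visit or staff. No change to product frequency is proposed.

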7.9 DESCRIPTION OF CONTROL PROCEDURES FOR MULTIPLICITY AND ADJUSTMENT OF ERROR PROBABILITIES

Not applicable.

7.10 SPECIFICATION OF SUBGROUPS FOR ANALYSIS

No subgroup analysis is planned to be made.

7.11 MANAGEMENT AND JUSTIFICATION OF MISSING, UNUSED OR SPURIOUS DATA, INCLUDING DROP-OUTS

No strategy for taking in charge missing data has been defined. Data that are not valid or missing will be considered and treated as missing data.

7.12 PROCEDURE FOR REPORTING DEVIATIONS FROM THE ORIGINAL STATISTICAL PLAN

Any modification to the statistical analysis plan due to a substantial modification of the CIP will be documented as an amendment and will be described in the final study report if applicable.

8- DATA MANAGEMENT

8.1 METHODS FOR DATA ENTRY AND COLLECTION

8.1.1 Identification of source data

Source data are all information in original records of clinical findings, observations, or other activities of the clinical investigation necessary for the reconstruction and evaluation of the clinical investigation.

The data related to the subjects' characteristics, to their current or previous medical state and to the safety of the device will be notified in the subject's source document and the eCRF.

Source data for photographs are acquisitions made at each kinetics and for each zone and will be saved on the device's specific software and then on Eurofins Dermascan internal network.

A list identifying the location of source data on each investigation site will be prepared by the CRO before the study start.

8.1.2 Data collection

At each visit of the subject, the investigator or delegate reports in the source document the data related to the subject's health state, and the safety and effectiveness of the device. These data are then reported in the subject's eCRF. Some effectiveness data are directly recorded within data capture software for measurement instruments and are not reported in the eCRF.

One source document and one eCRF must exist for each subject having signed an informed consent.

The eCRF is designed to identify each subject by a subject number and, where appropriate, subject's initials. The eCRF pages are validated by the principal investigator by electronic signature before data analysis. An eCRF guideline will be edited and distributed to investigational site.

8.1.3 Data entry

The solution used for the eCRF is the one from DataCapt.

8.2 PROCEDURES USED FOR DATA REVIEW, DATABASE CLEANING AND ISSUING/RESOLVING DATA QUERIES

8.2.1 Audit trail

The solution used for the eCRF contains an audit trail that will be extracted at the study end.

8.2.2 Data queries

Queries (missing data, inconsistencies...) will be edited by the CRA in charge of the monitoring directly in the eCRF. All queries must be answered before the database lock.

8.2.3 Medical coding

None.

8.2.4 Data Review

Data review will be performed by the project manager. Inconsistencies detected will be solved by the project manager or the concerned person.

The study review aims at determining the analysis population by:

- reviewing the conditions of study's realization,
- specifying all the CIP's deviations liable to lead the skew into statistical analysis,

DERMOSCIENCES FRANCE	Medical Device CIP # 22E2387	Final version 1.0 Date: 16.08.2022	Confidential Page 37/49
-------------------------	---------------------------------	---------------------------------------	----------------------------

- reviewing the statistical analysis plan if needed.

Following the data review, the statistical analysis populations will be defined and a report will be written and validated by the CRO and the sponsor.

8.2.5 Preparation of the Database and Locking

The database will be prepared in accordance with the data review conclusion.

The database will be locked upon resolution of all queries. A copy of the locked database will be sent to the sponsor certifying that the database has been locked. A signed database lock form will be provided.

After the database has been locked, any change to the database can only be done upon approval of the CRO and the sponsor. If the database needs to be corrected, unlocking/relocking must be clearly documented in the TMF (Trial Master File).

8.2.6 Data unblinding

Not applicable

8.2.7 Final Report

A final report according to ISO 14155:2020 will be written by the CRO project manager. A draft will be sent to the sponsor for validation. This final report will be signed by the coordinating investigator, the CRO, the biostatistician and the sponsor.

8.3 PROCEDURES FOR VERIFICATION, VALIDATION AND SECURING OF ELECTRONIC CLINICAL DATA SYSTEMS, IF APPLICABLE

An eCRF will be used for this study. eCRF conception and data-management will be managed with DataCapt which answers to all international regulatory requirements.

8.4 PROCEDURES TO MAINTAIN AND PROTECT SUBJECT PRIVACY

In this study, the CRO and investigation site will process personal data of subjects having signed a consent form on behalf of the sponsor, who is the data controller, in accordance with the rules of the protection of personal data and, in particular, the Regulation (EU) 2016/679 of the European Parliament and of the Council of 27 April 2016 on the protection of natural persons with regard to the processing of personal data and on the free movement of such data.

For this purpose, the CRO and investigation site commit themselves to only collect personal data which are needed for analysis and for the control of clinical data generated, by ensuring their security and integrity and by guaranteeing their confidentiality.

The CRO will make sure beforehand and throughout the duration of the data-processing:

- of the compliance with the obligations of the applicable data protection law,
- to inform subjects of their personal data-processing and obtain the prior consent for their collection,
- to implement and maintain appropriate technical and organisational measures.

To guarantee the confidentiality of collected data, the name and other information's allowing to identify the subject will not be included in the study results. Subject's will be identified only by a code composed of subject number and first letter of name and first name. Only the investigator and authorized personnel on site will be able to link this code to subject's name. The re-identification, if necessary, will be done according to a list or via this informed consent form which is kept and archived on site in the Investigator Site File (ISF). This list is only available on site and will not be sent to the CRO nor the sponsor.

According to Article 14 of GDPR, the concerned subject must be informed of the identity and the contact details of the controller and, where applicable, of the controller's representative.

In this clinical investigation, subject's may exercise their rights at any time from the investigator.

DERMOSCIENCES FRANCE	Medical Device CIP # 22E2387	Final version 1.0 Date: 16.08.2022	Confidential Page 38/49
-------------------------	---------------------------------	---------------------------------------	----------------------------

8.5 PROCEDURES AND PERIOD FOR DATA RETENTION

The sponsor must archive the CIP, documentation, approvals and all other essential documents related to the study, including certificates that satisfactory audit and inspection procedures have been carried out, for a duration of 15 years. Eurofins Dermascan Pharmascan will archive all documents concerning the study as detailed below:

- All documents must be archived in a secure place and treated as confidential material.
- Paper documents will be stored maximum during one year before being transmitted for archiving to an approved service provider or on site.
- Data will be archived securely as digital and/or paper version for 15 years from the date of dispatch of the final report's acceptance.

At the end of this period, the study archives will be destroyed unless otherwise stipulated in writing by the sponsor.

8.6 OTHER ASPECTS OF CLINICAL QUALITY ASSURANCE

In order to ensure the conformity of the studies entrusted to Good Clinical Practices (including Medical Devices' GCP as defined in ISO 14155:2020) and regulatory requirements, Eurofins Dermascan Pharmascan has implemented a quality management system which has been certified ISO 9001:2015.

9- AMENDMENTS TO THE CLINICAL INVESTIGATION PLAN

The sponsor or the principal investigator might modify the CIP for ethical, medical or scientific reasons. No change can be implemented at investigational sites without having obtained the favourable opinion of the sponsor, unless there is an immediate risk for the safety or well-being of the subjects.

These changes will be documented in the TMF and communicated to investigational sites as soon as possible.

If the modifications are considered as substantial by the sponsor (that are likely to have a substantial impact on the safety, health or rights of the subjects or on the robustness or reliability of the clinical data generated by the investigation), changes will be submitted to obtain the opinion of EC and approval of the President of the Polish Competent Authority (Urząd Rejestracji Produktów Leczniczych, Wyrobów Medycznych i Produktów Biobójczych).

10- DEVIATIONS FROM CLINICAL INVESTIGATION PLAN

The investigators are not allowed to deviate from the CIP, except under emergency circumstances, to protect the rights, safety and well-being of the subjects.

